13 DATA ANALYSIS AND STATISTICAL CONSIDERATIONS

13.1 Description of statistical methods

All statistical aspects of the study will be fully documented in a comprehensive Statistical Analysis Plan authored by the study statistician and agreed by the independent Trial Steering Committee.

The primary outcome will be an exploration of camostat safety and toxicity, in terms of the number and severity of AEs and SAEs.

Descriptive statistics will be used to describe the demographics for each randomised group and overall. For categorical data, frequencies will be reported, and for continuous variables means and standard deviations, or for skewed data, medians and interquartile ranges will be reported.

Secondary outcomes will be reported in a similar way to the demographic data, with an estimate of the difference and standard error between the treatment groups for continuous or ordinal scale data. Medians and IQRs will be used where data are non-normally distributed. Absolute percentage difference and standard error will be reported for binary variables. Kaplan-Meier plots and life tables will be used to estimate median survival times

Subgroups will be explored where there are sufficient patients in each group. Data will be split by age (< 65 years vs ≥ 65 years), fall in lymphocyte ($<20\%$ fall vs $\geq 20\%$ fall), and neutrophil:lymphocyte ratio (<2.18 vs ≥ 2.18) for key explanatory variables.

No significance testing will be performed. Differences between treatment groups will be reported solely to inform future trials.

All enrolled patients who receive at least one dose of camostat in the treatment arm and complete Day 1 in the control arm will be evaluable for safety.

In order to be evaluable for efficacy, treatment arm patients must receive camostat for a minimum of five days, and control arm patients must either complete up to Day 14 or come off trial at an earlier timepoint due to an endpoint (e.g. hospitalisation).

Safety data will be collected from the date of written, or verbal, consent. Safety variables will be summarised by descriptive statistics.

Adverse events will be reported as tables of frequency of AEs by MedDRA system organ class and by worst severity grade observed. Tables should indicate related and unrelated events

Adverse events will be reported for each arm and presented as tables of frequency of AEs by MedDRA system organ class and by worst severity grade observed. Tables should indicate related and unrelated events.

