5.1 Patient Populations

The analysis sets are defined as follows:

Full Analysis Population (FAP):	All enrolled patients.
	Patients who are enrolled in error onto the trial (due to ineligibility/administrative error), prior to receiving study treatment, will be excluded from the FAP.
Safety Population:	All enrolled patients who received at least one dose of camostat (or complete Day 1 of the control arm). Safety data will be collected from the date of written consent.
Efficacy Population:	Treatment arm patients must receive camostat for a minimum of five days, and control arm patients must either complete up to Day 14 or come off trial at an earlier timepoint due to an endpoint (e.g. hospitalisation).
Pharmacokinetic Population:	All enrolled patients who received one dose of camostat (or complete Day 1 of the control arm) – PK sample required (optional).

All other populations will be the same definition as Efficacy Population as defined above.

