6.7 Adverse Events

For patients on the treatment arm Pre-treatment AE's will be defined as those where "Did this AE start prior to first dose of IMP?" is ticked. Treatment Emergent AE's will be defined as those where "Did this AE start prior to first dose of IMP?" is not ticked. For patients on the control arm pre-treatment AE's will be defined as those where the AE started prior to Day 1. Treatment emergent AE's will be defined as those where the AE started after and inclusive of Day 1.

Treatment related AE's are those where causality to IMP is considered to be Possible, Probable or Highly Probable.

COVID-19 related AE's will be defined as those where "Is this AE related to COVID-19" is ticked yes.

The frequency of AEs will be summarised overall and by treatment arm. A patient can be counted multiple times per row for the No. of Episodes but will only be counted once per row for the No. of Patients.

Table 5: Frequency of All Adverse Events

Safety population

MedDRA System Organ Class (SOC) MedDRA Preferred Term	No. of Episodes Reported	No. of Patients N=XX	No. of Patients in Treatment Arm N=XX	No. of Patients in Control Arm N=XX
All AE's	N	N (%)	N (%)	N (%)
BLOOD AND LYMPHATIC...				
Anemia				
CARDIAC DISORDERS				
Sinus tachycardia				
Etc				

There will be additional versions of the above table based on pre-treatment AE's, treatment emergent AE's, treatment emergent SAE's (any AE that is considered Serious), related treatment emergent AE's. COVID-19 related AE's.

Overview of treatment emergent adverse events (by treatment arm). An AE is considered to have led to withdrawal if an adverse event with "Did the AE cause the subject to be discontinued from the study?" is recorded as yes.

Table 6: Overview of Treatment Emergent Adverse Events (Inclusive and post Day 1)

Safety population

Patients with TEAEs	Overall No. of Patients N=XX	No. of Patients in Treatment arm N=XX	No. of Patients in Control arm N=XX
Patients with >=1 TEAE	N (%)	N (%)	N (%)
Patients with >= 1 TE SAE			
Patients with >= 1 COVID-19 related			
Patients with >= 1 Treatment related			
Patients with >= 1 AE leading to withdrawal			
Patients who died			

Treatment emergent adverse events leading to withdrawal of treatment will be listed by patient. Patients will be included if an adverse event has "Action taken" recorded as "Drug Withdrawn" or "Did the AE cause the subject to be discontinued from the study?" is recorded as yes.

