6.10 General data conventions

Data will be grouped according to the assigned treatment arm, as specified in the study protocol. Patients who deviate from the assigned treatment arm will be clearly described in the CSR with regards to their treatment modification and if applicable in the list of protocol deviations (Section 5.2).

Continuous variables will be summarised and presented with summary statistics.

Categorical variables will be summarised in frequency tables. Percentages in the summary tables will be rounded and may therefore not always add up to exactly 100%.

The convention in Rave is that an unknown day resolves to 1st of the month and an unknown month resolves to January. Dates may be ordered by this, however CRUK do not perform calculations on unknown dates.

Durations of AEs: the start date of an AE is considered as Day 1 of the event and should be included in all duration calculations (i.e. if an AE starts and stops on same day, the duration should be reported as one day).

- For unrelated AEs, those with missing or partially completed end dates will not be excluded from analysis and the duration of the AE will remain as unknown.
- For related AEs, prior to final data lock, an end date will be either i) confirmed AE end date or ii) stabilisation of AE. If lost to follow-up then the AE would stay as not recovered/not resolved. In both these cases duration would not be calculated.

Time to onset of AEs from IMP administration: the time to onset should be calculated from the date of the first administration of IMP in the trial (e.g. Day 1). Onset time will be calculated as 0 if the AE occurs on the same day as the dose.

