11.1 Populations

The efficacy population will only include patients from the camostat arm where they have completed 5 days of treatment and in the control arm where they have completed 14 days of treatment or reached an endpoint (eg hospitalisation). All primary and secondary analyses will be conducted with this population. An intention-to-treat analysis of the main secondary outcomes (COVID-19 related hospital admissions, supplementary oxygen-free days, ventilator-free days, time to worst point on the 9-point ordinal scale) will also be conducted, should the data allow.

Patients who agree to the taking of blood samples will be included in the analysis of the PK data. The mean and SD will be reported at each time point (Days 7 and 14), as will the mean changes. The data may be log (or other) transformed if not normally distributed. [REDACTED]

[REDACTED] Change will be
change from previous blood test.

The safety population will include all patients with at least one dose of treatment (camostat or control). Safety data will be collected from the date of written consent. Safety variables will be summarised by descriptive statistics.

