12 LIST OF ANALYSES

Although the sample size has been calculated on recruitment rate, the primary outcome will be the comparison of adverse events and their severity between treatment arms. These will be listed overall and by strata.

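### The analysis plan groups all data by assigned arm with no exception for safety, so a control patient who took camostat would have adverse events counted under best supportive care

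*SAP*

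**What the plan says.** The SAP document consists of the RAP (sections 1 to 9) and an appended statistical analysis plan (sections 10 to 13).

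- **Grouping rule.** RAP 6.10: "Data will be grouped according to the assigned treatment arm, as specified in the study protocol". It continues: "Patients who deviate from the assigned treatment arm will be clearly described in the CSR with regards to their treatment modification", and where applicable they also appear in the list of protocol deviations.
- **Safety population.** RAP 5.1 and 6.6 and SAP 11.1 define who is included: at least one camostat dose, or in the control arm completion of Day 1 (SAP 11.1 speaks of a dose of control). None says in which column an included patient is counted.
- **AE tables.** RAP 6.7: "The frequency of AEs will be summarised overall and by treatment arm". Tables 5 and 6 have a treatment-arm and a control-arm column. Treatment-emergent status also follows the arm: first dose of study drug in the treatment arm, Day 1 in the control arm.
- **Primary outcome.** SAP section 12: "the primary outcome will be the comparison of adverse events and their severity between treatment arms".
- **Protocol.** Section 13.1: "Adverse events will be reported for each arm and presented as tables of frequency of AEs by MedDRA system organ class". It does not say whether arm means assigned or received.

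**The concern.** Grouping by assignment is the right default for baseline and intention-to-treat efficacy tables. For toxicity it can credit a drug's events to patients labelled untreated. Here the AE comparison is the primary outcome, and Table 6 has a row for treatment-related events with a control column, so an event judged related to camostat could be counted under best supportive care.

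The narrative in the study report would explain such a patient but would not move the counts. It also does not reach the registry: RAP section 7 says that the registry tables are kept out of the study report, so a reader of the section 7.3 tables would see only the counts.

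**Working it through.** **1. Does any text override the general rule?** The plan has no figure on this point to reproduce, so the first check is textual.

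| Place | What it settles | Column for a control who took camostat |
|---|---|---|
| RAP 6.10 | Grouping of data in general | Assigned arm (control) |
| RAP 5.1, 6.6; SAP 11.1 | Membership of the safety population | Not stated |
| RAP 6.7, Tables 5 and 6 | AE tables by arm | Not stated |
| Protocol 13.1 | AEs reported per arm | Not stated |

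No rule for grouping by treatment received appears anywhere, so the general convention governs and the patient is counted under control. The reverse case does not arise: a camostat-assigned patient who takes no dose does not enter the safety population.

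**2. Effect of one patient.** Input: up to 50 patients per arm (RAP section 4); assume all 50 are in the safety population. Each exposed control with an AE adds 1/50 = 2.0 points to the control column; two such patients add 2/50 = 4.0 points.

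**3. Average effect.** Let k of the 50 controls take camostat, with AE risk pT on camostat and pC without it. Grouped by assignment, the expected difference is

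pT − [(50 − k)·pC + k·pT]/50 = (pT − pC)·(1 − k/50).

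The values of k, pT and pC are assumptions; the documents give none.

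| k | 40% vs 20% | 10% vs 0% | 30% vs 30% |
|---|---|---|---|
| 0 | 20.0 points | 10.0 points | 0.0 points |
| 1 | 19.6 | 9.8 | 0.0 |
| 2 | 19.2 | 9.6 | 0.0 |
| 5 | 18.0 | 9.0 | 0.0 |

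For k = 2 at 40% vs 20%, the control column is (48 × 0.20 + 2 × 0.40)/50 = 10.4/50 = 20.8%, and 40.0 − 20.8 = 19.2 points.

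**4. Single realisations, two exposed controls.** Assume 20 of the 50 camostat-assigned patients have an AE, and 10 of the 48 unexposed controls.

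- *Both exposed controls have an AE.* By assignment: 20/50 − 12/50 = 16.0 points. By treatment received: 22/52 − 10/48 = 42.3% − 20.8% = 21.5 points. Assignment understates the difference by about 5.5 points.
- *Neither has an AE.* By assignment: 20/50 − 10/50 = 20.0 points. By treatment received: 20/52 − 10/48 = 38.5% − 20.8% = 17.6 points (from unrounded values). Assignment shows the larger difference.

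The direction is therefore a statement about averages, not about every data set.

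**The case against.** The strongest reply is that the event is improbable and would be visible.

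- **Likelihood.** The trial is open label and patients are told their arm (protocol 5.3.1). Only treatment-arm packs contain tablets (9.1.1), dosage is double-checked before dispensing (7.2.5) and tablets are accounted for (7.2.6). Camostat is not approved in the EU (3.1), and co-enrolment in another drug trial is excluded (6.2). This stands: zero crossover is quite possible.
- **Visibility.** Causality is judged event by event (protocol 12.2), wrong dose or schedule is a reportable deviation (RAP 6.4), AEs are listed by subject (RAP 8.1) and Table 5 has an overall column. A camostat-related event under control would be conspicuous. This limits the harm but does not correct the by-arm counts or the registry tables.
- **Text.** RAP 6.10 does not name the safety tables. Elsewhere the RAP refers explicitly to the randomised arm (6.2, 6.3, Table 10), whereas 6.7 says only treatment arm. This shows that the plan did not openly choose assigned-arm grouping for safety. It does not displace the general rule.

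A reader might also infer that the plan expects crossover because it provides for patients who leave their assigned arm. The documents do not support that. The sentence is a contingency, and it speaks of treatment modification, a term that RAP 6.5 uses for a table restricted to the treatment arm; it may mean no more than dose changes or non-compliance. Nor does grouping by assignment create an inclusion anomaly: a control who completes Day 1 is in the safety population whether or not camostat was taken.

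**Conclusion.** The point holds as a minor one. The stated convention, with no safety exception, would put a camostat-exposed control in the wrong column of the by-arm AE tables. It matters only if such a patient exists, and the documents give no reason to expect more than very few.

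The size rests on an assumed 50 per arm and assumed AE risks. Each exposed control with an AE adds 2.0 points to the control column; the average shrinkage for two exposed controls is 0.8 points (20.0 to 19.2) at 40% versus 20%.

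Two stronger readings should be avoided. A 4-point rise in the control column from two patients is not the typical effect; it requires both to have an AE. And the rule does not always hide toxicity: the shift is towards no effect on average if camostat raises AE risk, but individual data sets can go the other way. The protocol plans no significance testing (13.1), so the consequence is a misleading descriptive count, not a wrong test result.

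**What to change.** Add to RAP 6.10, and mirror in SAP 11.1:

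*Arm-split safety outputs (Tables 5 and 6, the laboratory Tables 8 and 9, the section 7.3 tables and the primary outcome in section 7.4) are grouped by treatment received. Any patient who took at least one dose of camostat is shown in the camostat column. Baseline and efficacy tables remain by assigned arm.*

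Table 7 needs no change, because it lists patients without an arm column.

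Align RAP 6.7 so that treatment-emergent status for any patient who took camostat runs from the first dose, whichever arm was assigned. Otherwise an exposed control's event after Day 1 but before the first dose would still count as treatment-emergent, now in the camostat column.

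The cost is a few sentences, one variable for actual treatment and a small change to the treatment-emergent derivation. If crossover occurs, the safety denominators change (for two patients, 52 and 48 instead of 50 and 50) and those patients are no longer compared as randomised. If nobody crosses over, every table is identical. Writing the rule now also avoids deciding it after the fact in an open-label trial.

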6.11 Decimal places

When data is used in calculations it is important that rounding is only conducted when the final test result is obtained (to avoid accumulation of errors).

All percentages should be presented to 1 decimal place. If a percentage value is less than 0.1% on rounding, then use '<0.1%'.

Days to be presented to 0 decimal places.

6.12 Statistical software

Medidata Rave will be used as the Electronic Data Capture (EDC) system for the trial.

Any statistical software should be defined.

SAS version 9.4 will be used to generate data listings and summary tables/graphs, as well as any statistical analysis as per the trial SAP.

6.13 Supplementary analysis (data collected outside of the clinical database)

6.13.1 Pharmacokinetics

Clinical study objectives	Description of clinical study endpoint	Sample used for this endpoint
Secondary Objective: To confirm that the PK profile aligns with the established PK profile for the active metabolite of camostat, 4-(4-Guanidinobenzoyloxy)phenylacetic acid (GBPA).	
 Confirm PK parameters of GBPA camostat as assessed by population estimates from population PK analysis (popPK). 	
 PK plasma

Pharmacokinetics analysis will be described in analytical laboratory reports included in appendices. PK population only.

Interim reports will be received as agreed by CRUK with final reports at the end of the trial.

6.13.2 Tertiary/research endpoint/s

Clinical study objectives	Description of clinical study endpoint	Sample used for this endpoint
[REDACTED]	[REDACTED]	[REDACTED]

[REDACTED]	[REDACTED]	[REDACTED]
	[REDACTED] negative swabs by qPCR.	
[REDACTED]	[REDACTED]	[REDACTED]
	[REDACTED]	

Please see Appendix 1 for full Statistical Analysis Plan, Version 1.0 dated 27Sep2021

6.14 Other statistical analysis

7 CLINICALTRIALS.GOV

The following tables illustrated for the Clinicaltrials.gov will not be part of the Clinical Study Report (CSR) and will be used for the upload of data to Clinicaltrials.gov only.

7.1 Arms and Interventions

The trial will be presented as a randomised trial.

Intervention Details: Patients will be randomised 1:1 into two arms.

Treatment arm: Patient to receive treatment with camostat tablets, 200mg four times daily (*qds*) for 14 days

Control arm (non-treatment): Patient to receive best supportive care.

Drug: Camostat

7.2 Participant Flow

The participant flow section of the results upload will include the following details. Tables will be programmed for Randomised Phase and Treatment Phase for all patients.

Lines with text in blue are required rows from clinicaltrials.gov

Period Title	Overall Study	Control arm	Programming notes
Arm/Group Title	Treatment arm		
Arm/Group Description	Patient to receive treatment with camostat tablets, 200mg four times daily (qds) for 14 days	Patient to receive best supportive care	
	Number of Participants	Number of Participants	Day 1
Started			
<to add trial milestone>			
<to add trial milestone>			
<to add trial milestone>			
Completed			Complete up to and including Day 14

Not completed		Patients started Day 1 and did not complete up to and including Day 14
Adverse Event / Serious Adverse event		
Death		
Lack of Efficacy		
Lost to Follow-up		Investigator withdrawal of consent / Investigator withdrawal of subject
Physician Decision		
Pregnancy		
Protocol Deviation		
Withdrawal by Subject		Subject withdrawal from treatment (treatment arm) / subject withdrawal (allows FU) (control arm) as well as subject withdrawal of consent (all patients)
Recovered		
Other		

Number of patients started is defined as: Day 1

Number of patients Completed is defined as: Day 14

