5.3.4 Day 7 visit

It is intended that the Day 7 interaction with the patient is made by a clinical professional who can assess whether the patient has recovered. Patients may be visited at home on Day 7 (to collect research bloods and [REDACTED] as well as receiving the daily video (phone) call. If at this visit/during the call, it is assessed that the patient (on the treatment arm) has recovered, the patient may be asked to discontinue with camostat administration, and the drug will be disposed of as per an approved process. Follow up calls and visits as per protocol will continue.

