10 DEFINITION OF END OF TRIAL

It is the responsibility of the Sponsor to inform the MHRA and the REC within 90 days of the End of Trial (EoT) that the trial has closed.

In cases of early termination of the trial (for example, due to toxicity) or a temporary halt by the CDD, the CDD will notify the MHRA and the REC within 15 days of the decision and a detailed, written explanation for the termination/halt will be given.

Recruitment will cease when:

- Camostat is considered too toxic to continue before the required number of patients have been recruited.
- The stated number of patients to be recruited has been reached.
- The stated objectives of the trial are achieved.
- The stated objectives of the trial are unlikely to be met based on emerging data from camostat trials worldwide, and it is confirmed the trial is to stop due to futility (end of trial will be the date of this decision).
- The stated objectives of the trial are likely to be met based on emerging data from camostat trials worldwide, and it is confirmed the trial is to stop due to efficacy proven elsewhere (end of trial will be the date of this decision).

Regardless of the reason for termination, all data available for patients at the time of discontinuation of follow-up must be recorded in the electronic/case report form (e/CRF). All reasons for discontinuation of treatment must be documented.

In terminating the trial, Investigators must ensure that provision is made to ensure appropriate ongoing care for the patient.

The End of Recruitment is defined as the date the last patient is recruited.

The End of Trial is defined as the date when the Day 28 data has been obtained for the last patient or the final follow-up visit or, if the trial is closed due to emerging data from camostat trials worldwide, the date of the Sponsor's decision to close the trial (whichever is the latter).

For analysis and reporting plans, please see Section 13.

To note: If camostat related SAEs are still ongoing at the EoT point, these will continue to be followed up as per protocol.

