6.3 Patient withdrawal / Completion

Reasons for patient withdrawal will be provided as the data is available and presented for each randomised treatment arm.

Table 2: Reasons for patient withdrawal / completion

Reason off study	No. of Patients (N=XX)	Patient Number (patients who withdrew only)	No. of patients in Treatment arm	No. of patients in Control arm
Completion of treatment / monitoring period	XX (%)		XX (%)	XX (%)
Recovered				
Adverse event/Serious adverse event				
Pregnancy				
Death				
Investigator withdrawal of subject				
Subject withdrawal of consent				
Subject withdrawal from treatment (treatment arm) / subject withdrawal (allows FU) (control arm)				
Protocol deviations				

Sponsor's decision to terminate the trial				
Other				
Lost to follow up				

Full Analysis Population

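### The registry participant-flow table is labelled as the whole study, but it counts completion at Day 14 and mixes stopping camostat with leaving follow-up

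*SAP*

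**What the plan says.** SAP 7.2 (Participant Flow) gives one shell, with the period title "Overall Study". Below it stands "Number of patients Completed is defined as: Day 14". The programming note for the Not completed line reads "Patients started Day 1 and did not complete up to and including Day 14", and Recovered is one of the reasons listed beneath it. The note for the Withdrawal by Subject row pools three things: stopping treatment in the camostat arm, control withdrawals that still allow follow-up, and withdrawal of consent. The introductory text of the same section says "Tables will be programmed for Randomised Phase and Treatment Phase for all patients", but no shell carries either of those titles.

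SAP 6.3, Table 2, has a similar structure. Under a *Reason off study* heading it lists finishing the treatment or monitoring period, Recovered, and "Subject withdrawal from treatment (treatment arm) / subject withdrawal (allows FU) (control arm"), alongside consent withdrawal and loss to follow-up.

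Protocol 5.3.4 says that if a treatment-arm patient "has recovered, the patient may be asked to discontinue with camostat administration", and then: "Follow up calls and visits as per protocol will continue". Protocol 11 says that a decision to stop trial treatment is not to be taken as withdrawing consent to follow-up. Protocol 10 ties the end of the trial to Day 28: "The End of Trial is defined as the date when the Day 28 data has been obtained for the last patient" (with alternatives for a final follow-up visit or early closure).

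**The concern.** A participant-flow table tells a reader who was still under observation when the outcomes were measured. Here the label says whole study, the cut-off is the end of the 14-day treatment and daily-call period, and the reasons for non-completion include events after which the protocol keeps the patient in the study.

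Two errors can follow, in opposite directions. Patients who stop camostat because they are well, and who are followed to Day 28, can appear as attrition. The protocol writes the recovery stop for the treatment arm only, and the SAP does not say what Recovered means for a control, so the arms may not be counted alike. Conversely, non-fatal loss after Day 14 has no row in the flow table.

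At stake is how the registry record, and through Table 2 the study report, describes retention. SAP 12.1 names retention as a feasibility measure, and the trial is meant to inform later ones.

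**Working it through.** The plan states no completion figure to reproduce. The check follows typical patients through the definitions.

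**Inputs.**
- Completion point: Day 14 (SAP 7.2).
- Contacts after Day 14: Days 21 and 28 (protocol 5.1 and 8.3.3).
- Adverse-event collection: to 28 days from Day 1 (SAP 7.3).
- Time frame of the primary and clinical secondary outcome measures: Days 1-28 (SAP 7.4).
- Arm size: up to 50 (SAP section 4).

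The days after the completion point are 28 − 14 = 14, which is 14/28 = 50% of the outcome window.

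**Classification.** The SAP does not say what must be completed to Day 14. Reading A takes it as the camostat course (monitoring in controls). Reading B takes it as monitoring in both arms.

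| Patient | Reading A | Reading B | Day 28 status obtained? |
|---|---|---|---|
| Camostat, stops at Day 7 as recovered, followed to Day 28 | Not completed | Completed | Yes |
| Camostat, chooses to stop drug before Day 14, followed to Day 28 | Not completed | Completed by the definition, but the row note sends the patient to Withdrawal by Subject | Yes |
| Either arm, finishes 14 days, lost or withdraws on Day 20 | Completed | Completed | No |
| Either arm, finishes 14 days, dies on Day 20 | Completed | Completed | Died |
| Camostat, stops at Day 7 as recovered, lost on Day 20 | Not completed | Completed | No |

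Reading A is the more natural, because a Recovered row under Not completed would have little use on reading B. The third and fourth lines do not depend on the reading: the Day 14 cut-off misdescribes them either way.

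The first patient, having taken at least five days of camostat, is in the efficacy population (SAP 5.1). The plan can therefore analyse as evaluable someone whom the flow table shows as not completing.

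**Illustration.** Let *r* be the share of camostat patients who stop as recovered but are followed, and *l* the share of each arm lost on Days 15-28. Neither is in the documents; both are assumptions. Take 50 per arm, no other attrition, and no control coded Recovered.

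- Day 14 rule, reading A, camostat: (50 − 50*r*)/50. For *r* = 10%, 30%, 50% this is 45/50 = 90%, 35/50 = 70%, 25/50 = 50%, so 5, 15 or 25 followed patients are shown as non-completers.
- Day 14 rule, reading B, camostat: 50/50 = 100% for any *r*.
- Day 14 rule, control, either reading: 50/50 = 100% for any *l*.
- Day 28 rule, both arms: 1 − *l*. For *l* = 0%, 5%, 10% this is 100%, 95%, 90%, for any *r*.

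The apparent gap between arms is thus *r* on reading A and zero on reading B. Any control coded Recovered would narrow it. Under the Day 28 rule, *r* drops out and *l* becomes visible.

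**The case against.** The strongest reply is that the fault may lie in the label rather than the rule. Day 14 is a sensible end for a treatment period, SAP 7.2 promises a Treatment Phase table, and the blank milestone rows show that the shell is unfinished. The definition also leaves room for reading B. This stands as far as it goes, but it does not remove the problem: the only shell is for the overall study, and two programmers could build different tables from it.

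A second reply is that the information is not lost:
- Deaths appear in the all-cause mortality table (SAP 7.3) and in Table 6.
- Table 2 has a row for loss to follow-up and states no Day 14 limit.
- SAP 8.1 plans an end-of-study listing.
- SAP 6.1 promises reasons for treatment discontinuation.
- Table 7 separates withdrawal from drug and withdrawal from study for adverse events.

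This also stands. The gap is specific: non-fatal loss after Day 14 is missing from the flow table, and stopping treatment is not separated from study exit there or under the Table 2 heading.

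Third, section 7 serves the registry upload only, and a row labelled Recovered tells a careful reader that these are not losses. Both are fair and limit the importance of the point. Table 2 does belong to the study report.

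A reader might infer more: that the plan will show a large excess of attrition on camostat, that it conceals later losses, or that every patient lost on Days 15-28 is counted as complete. The documents support none of these. They give no recovery-stop rate, and stopping at Day 7 is discretionary. Later losses and deaths have other places to appear. On reading A, a patient who stopped early as recovered and was lost later is already a non-completer.

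**Conclusion.** The point holds as a fault of definition and labelling in two tables. The overall-study flow in SAP 7.2 uses a Day 14 completion point and treatment-stop reasons that conflict with protocol 5.3.4, protocol 11 and the Day 28 follow-up. The misstatement of Days 15-28 follows on either reading. The misclassification of recovered patients follows on the most natural reading, but the wording does not settle it.

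The size is unknown. The 5 to 25 patients per 50 rest on assumed recovery-stop rates of 10-50% and on reading A; on reading B the figure is zero. No endpoint estimate or analysis population changes. The correction is worth making because the present rule gives wrong study-completion counts and costs little to put right.

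**What to change.** In SAP 7.2, for the overall-study period:
- Define Completed in both arms as Day 28 status obtained, including the delayed Day 28 visit that protocol 8.3.4 allows for patients in hospital at that time.
- Keep deaths by Day 28 in the existing Death row under Not completed.
- Reserve the Not completed reasons for leaving the study before Day 28. Remove Recovered from them, and limit Withdrawal by Subject to patients who leave follow-up.
- Show completion of 14 days of camostat or monitoring, and stopping camostat as recovered with follow-up continuing, in the blank milestone rows or in the promised Treatment Phase table, where Day 14 belongs. State there whether drug or monitoring is meant.

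In SAP 6.3, split Table 2 into reasons for stopping camostat (treatment arm only, including Recovered) and reasons for leaving the study (both arms).

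The cost is reprogramming two tables. No new data should be needed, since SAP 8.1 already plans separate listings for treatment compliance, end of monitoring and end of study. This assumes that the end-of-study record holds the date and reason.
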